## Medtronic Controlled Information

## 9.2. Subject Screening

Subjects may be recruited through the investigator's practice and referring physicians. Potential subjects may be identified through chart reviews or as new or existing patients attend clinic visits as appropriate. If subjects are referred from outside the investigator's practice, sites are to ensure that appropriate release for access to the subject's records (paper and/or electronic) is obtained. Any subject recruitment materials disseminated to subjects (advertisements, handouts, posters, social media) must be approved by the IRB/EC prior to use.

All subjects must be consented in accordance with the protocol prior to any study-specific procedures. Recruited subjects will be screened by the Principal Investigator or authorized site personnel by reviewing the study's inclusion and exclusion criteria.

A pre-screen (recruitment) log will be completed for all subjects screened but not consented for the study. No subject-specific information will be collected on this log, only the date of review and the reason for the screen failure.

A screening log will be completed by the site to maintain a cumulative log of all screened subjects with reason for any screening failures.

The Investigator will maintain a listing of all subjects enrolled in the study.

## 9.3. Subject Consent

Informed consent should be obtained in written format and using a form approved by the local IRB/EC, if applicable. The form should contain standard language consistent with local policies for ensuring privacy of confidential information. The informed consent process will be performed in accordance with the ethical principles that have their origin in the Declaration of Helsinki, 21CFR§50 Protection of Human Subjects (US only), SOR/98- 282 (Canada only) and in accordance with local regulatory requirements. No vulnerable patients will be allowed to be consented to participate in the study. Data will be collected and treated in accordance with applicable Data Privacy Legislation. With regard to the EU, this includes Directive 95/46/EC and subsequent legislation.

Prior to entering the study, the Principal Investigator or qualified designee will explain to each subject the purpose and nature of the study, procedures, expected study duration, available alternative therapies, and the benefits and risks involved with study participation and the potential treatment. The person obtaining consent will avoid any coercion or undue improper influence on, or inducement of, the subject to participate and the ICF will not waive, or appear to waive, any legal rights. Subjects will be given a copy of the IRB/EC approved ICF and will have ample time to review the document and to ask questions and will be informed of their right to withdraw from the study at any time without prejudice; ICFs will be provided in a language understandable to the subject. After this explanation and before any

**Medtronic Controlled Information**

study-specific procedures have been performed, the subject will voluntarily sign and personally date the ICF. Prior to participation in the study, the subject will receive a copy of the signed and dated written informed consent and any other written information provided to the subject.

The Principal Investigator or qualified (delegated) designee will document the informed consent process, including the date of consent and name of the person conducting the consent process in the subject's medical record. A copy of the signed ICF will also be placed in the subject's medical record. Throughout study participation, any significant new information will be provided to the subject as outlined in the informed consent form. As appropriate, the ICF may be revised based on new information that becomes available.

[REDACTED]

[REDACTED]

[REDACTED]

## 9.5. Assessment of Efficacy

Subject assessments will be administered by appropriately trained, qualified and delegated site personnel according to the usual practices of the site. Subjects will complete the study questionnaires confidentially on paper forms without site personnel consultation during the visit and these data will be entered to OC/RDC by site personnel. Bowel and Voiding Diaries should be completed prior to or directly after the follow-up visit when data are collected. Site personnel should review forms for completeness.

### Overactive Bladder Quality of Life Questionnaire (OAB-q)

The Overactive Bladder Quality of Life Questionnaire (OAB-q) is a 33-item validated questionnaire that was developed to assess symptom bother and the impact of overactive bladder (OAB) on health-related quality of life (HRQL). The questionnaire used in the current study includes a 4-week recall for symptom assessment. The questionnaire may also be used to drive health state utilities.

This questionnaire will be completed by the subject at Baseline, Three-month, Six-month, One-year, and Two-year Follow-up Visits.

### Cleveland Clinic Incontinence Score

The Cleveland Clinic Incontinence Score (Wexner Score) is an established 5-item questionnaire that was developed to assess the frequency and severity of fecal incontinence.

This questionnaire will be completed by the subject at Baseline, Three-month, Six-month, One-year, and Two-year Follow-up Visits.

---

### **Medtronic Controlled Information**

## Urinary Voiding Diary

Symptoms related to OAB and NOUR will be evaluated using either paper or electronic voiding diaries. Subjects will be trained to complete the urinary voiding diaries for 3-days for OAB with diary details collected (such as time, type of episode, urgency, sleep/awake status, etc.) and for 7-days for NOUR with diary details collected (such as time, type of episode, volume, etc.) as part of the baseline procedures. The urinary voiding diaries will be completed for 3-days for OAB and 7-days for NOUR towards the end of the therapy evaluation and prior to each subsequent follow-up visit. Every effort should be made to remind subjects of the importance of real-time diary completion.

## Bowel Diary

Symptoms related to FI will be evaluated using either paper or electronic voiding diaries. Subjects will be trained to complete the bowel voiding diary for 7-days as part of the baseline procedures with diary details collected (such as time, type of episode, urgency, sleep/awake status, etc.). The bowel diaries will be completed for 7-days towards the end of the therapy evaluation.

Every effort should be made to remind subjects of the importance of real-time diary completion.

Term	Percentage
GDP	100%
Inflation	100%
Interest rates	100%
Central bank	100%
Monetary policy	100%
Quantitative easing	100%
Inflation targeting	100%
Interest rate hike	100%
Interest rate cut	100%
Interest rate parity	100%
Nominal interest rate	100%
Real interest rate	100%
Nominal GDP	100%
Real GDP	100%
Nominal exchange rate	0%
Real exchange rate	0%
Nominal income	100%
Real income	100%

## 9.6. Assessment of Safety

All reportable adverse events (see Section 11.1) and device deficiencies will be collected throughout the study once the informed consent form is signed until the subject is exited from the study.

## 9.7. Recording Data

Oracle Clinical Remote Data Capture (RDC)

This study will be conducted using a remote data capture system. The Oracle Clinical (OC) Remote Data Capture (RDC) system which allows the study centers to enter study data into the sponsor's database over a secure internet connection, will be used to capture study required Case Report Form (CRF) information. Data reported on urinary voiding diaries and subject questionnaires will be entered into the database by site personnel. Subjects will complete the study questionnaires confidentially on paper forms without site personnel consultation and these data will be entered to OC/RDC by site personnel.

Electronic CRFs (eCRFs) will be provided by the sponsor; required data will be taken from source documents and directly entered into the study database via the eCRFs by the site personnel, in accordance with applicable regulations.

The Principal Investigator, Sub-Investigator, or an individual delegated by the Principal Investigator on the Delegation of Authority and Signature Form, are responsible for documenting and entering data for the study on the eCRFs. The Principal Investigator or Sub-Investigator is required to approve all data on eCRFs via electronic signature.

## Urinary Voiding Diaries & Bowel Diaries

Symptom data for this study will be collected using either electronic or paper diaries.

### **Electronic Diary**

Electronic diaries may be provided by the sponsor for US study centers; the electronic diary collects details associated with symptoms for each episode. The system contains reminders and allows subjects to collect real-time voiding behavior onto a secure server. The system controls user access and maintains an audit trail. The information in the diary is de-identified and the data transmission contains two points of encryption. The de-identified data export files will be filed in the subject's medical record.

### **Paper Diary**

A paper diary is also available for use in the study. If a paper diary is used, the data will be entered to the RDC database by center personnel. Center personnel may not complete the diary for subjects except for data fields confirmed by the subject as documented within source documentation.

Diaries are to be completed only by the subject. Representatives from the research site may not make entries to the diaries or questionnaires except for data fields confirmed by the subject as documented within source documentation.

## **9.8. Deviation Handling**

Protocol deviations are digressions from the written protocol defined as an event where the clinical investigator or site personnel did not conduct protocol-required procedures according to the study protocol. The investigator is not allowed to deviate from the CIP, except under emergency circumstances to protect the rights, safety and well-being of human subjects. The investigator or delegated site personnel should contact the designated Medtronic study personnel to discuss the impact of the potential deviation. Site personnel should work with subjects to ensure subject follow-up visits are scheduled within the visit window. All protocol deviations must be reported on the Protocol Deviation eCRF promptly after the site's awareness of the deviation and submitted to the IRB/EC and CA(as required). Any deviations resulting in signification updates to the clinical investigational plan will require CA notification and/or approval, where required.

Deviations will be reviewed by Medtronic on an ongoing basis. The sponsor may choose to terminate the study at a site for failure to follow the written protocol and investigator agreement. If this occurs, the Investigator, IRB/EC and governing competent authority (if applicable) will be notified in writing of the reasons for the termination.

---

### **Medtronic Controlled Information**

## 9.9. Subject Withdrawal or Discontinuation

Subjects are free to voluntarily withdraw from the study at any time and for any reason. All implanted subjects will be followed until the Two-year Follow-up Visit, unless withdrawn from the study.

Withdrawn or exited subjects will be followed under normal medical practice.

Examples of reasons for study discontinuation include, but are not limited to, those listed below:

- Subject death
- Subject lost to follow-up
- Subject voluntarily withdraws from the study
- Investigator terminates the subject's participation in the study due to lack of compliance, violation of/change in eligibility criteria
- Any clinical laboratory abnormality, current illness, or other medical condition or situation occurs such that continued study participation would not be in the best interest of the subject.
- Normal study completion

Prior to deeming a subject lost to follow-up, telephone calls must be documented in the subject's medical record. If a minimum of three attempts to contact the subject have failed (e.g. phone and mailed letter), and no response is received, the site should exit the subject and complete the Study Exit eCRF.

When a subject is withdrawn from the study, the Study Exit eCRF is to be completed and should include detailed notes as to why the subject was withdrawn from the study (e.g., discomfort, lack of efficacy, diary too burdensome). Withdrawn subjects will not be replaced.

Once a subject completes participation in the study, follow-up will continue in accordance with the site's standard of care. No study specific medical care will be provided for a subject after discontinuation from the study, unless outlined in the Clinical Trial Agreement and Informed Consent Form.

## 10. Risks and Benefits

### 10.1. Potential Risks

The risks outlined below are the same risks found in commercial use of InterStim Micro System. No study specific risks are present. The clinical investigation has been designed to involve as little pain, discomfort, fear and any other foreseeable risk as possible for the subjects, and both the risk threshold and the degree of distress are specifically defined in the clinical investigation plan and constantly monitored.

### **10.1.1. Risks Outlined in the Instructions for Prescribers (IFP)**

Refer to the appropriate Information for Prescribers (IFP) manual for the InterStim Micro System components for an updated list on contraindications, precautions, warnings, adverse events, directions for use and other product specific details on the InterStim Micro System.

The risk level for the devices and implant procedure is the same if the subject is in this clinical trial or not. Certain adverse events may necessitate surgical intervention. For a comprehensive summary of adverse events, refer to the Information for Prescribers manual.

There might be other discomforts and risks related to an InterStim Micro System implant, sacral neuromodulation therapy with the InterStim Micro System and/or this study that are not foreseen at this time.

The following inconveniences may occur due to participation in the study:

- The time needed to complete your study diary may be an inconvenience
- You may find some of the questions or completing the study diary embarrassing

### **10.2. Potential Benefits**

Subjects will not receive any direct medical benefit from participation in this study. Participation in this study will not provide greater benefit than if the subject was receiving an InterStim Micro System implant and sacral neuromodulation therapy with the InterStim Micro System outside of the study. Information from this study might help researchers further understand the InterStim Micro System. The benefit to subjects participating in this study, and to future patients, resides in the knowledge gained from this study.

### **10.3. Risk-Benefit Rationale**

Participation in this study will not expose the subject to greater risks than if he/she were receiving an InterStim Micro System implant and sacral neuromodulation therapy with the InterStim Micro System outside of the study.

The risks associated with an InterStim Micro System implant and sacral neuromodulation therapy with the InterStim Micro System are minimized in this study by selecting only qualified Investigators experienced in sacral neuromodulation, selecting an appropriate patient population via inclusion/exclusion screening, and monitoring subject progress and events reported for this study. The review and minimization of the potential risks to the patient and the potential benefits to the patient support the conduct of this study.

## 11. Adverse Events and Device Deficiencies

### 11.1. Definitions/Classifications

Any adverse event meeting the definition of: serious adverse events and/or adverse device effects as well as all device deficiencies will be considered reportable for this study and will be collected after the subject is consented to participate in the study through study exit. The term “investigational device” is part of ISO 14155:2011 definitions. The term “investigational device” refers to any device used in the study including market released devices.

Reportable adverse event terms are defined as follows:

- Device Related: An adverse event that results from the presence or performance (intended or otherwise) of any component of the InterStim Micro System
- Procedure Related: An adverse event that occurs due to any procedure related to the implantation or surgical revision of the InterStim Micro System. The procedure is defined as the lead placement, neurostimulator implant procedure and surgical revision (including explant procedure).
- Therapy Related: An adverse event related to therapy delivery by device e.g. device stimulation issue (normally therapy-related events resolve when the device is turned off or reprogrammed).

Adverse events that are classified as possible, probable or causal are considered to be related for analysis purposes.

The following are not adverse events:

- Any normal expected postoperative (implant or revision) complaints or symptoms unless the event involves a clinically significant change in severity or duration of symptoms or requires clinical intervention that is different from ordinary postoperative care. Expected postoperative outcomes include headache, incisional pain, nausea, vomiting, low grade fever, oozing at dressing, dizziness, irritability, sleepiness, nervousness, insomnia, constipation, urinary retention, confusion and similar events.
- Any non-clinically significant, transient (lasting for only a short time) stimulation-related effects that occur during the implant/revision procedure, programming and follow-up period.
- Worsening of OAB, FI and/or NOUR symptoms will be collected as part of the study objectives and/or additional measures and are not considered a reportable adverse event.

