## **8.2. Subject Enrollment**

Each subject must meet all the inclusion criteria and no exclusion criteria for one of the three study cohorts to be eligible to participate in the study. Each subject will only be enrolled in one study cohort.

Subjects are considered enrolled at completion of the neurostimulator implant procedure. Any subject not meeting eligibility criteria will be excluded from study participation. Site personnel must complete logs related to recruitment and enrollment as required by the study.

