**Table 9-1: Study Procedures**

	Baseline	Evaluation Lead Implant	Tined Lead Implant** / Neurostimulator Implant	Follow- up Visits	Unscheduled Visit	Surgical Revision
All Cohorts						
Informed Consent*	X					
		█				
Pregnancy Assessment	X					
		█	█			
		█	█			
		█	█			
				█	█	█
				█		
				█		
				█		
				█		
Assessment of Reportable Adverse Events and Device Deficiencies	X	X	X	X	X	X
Overactive Bladder						
OAB-q Questionnaire	X			X		
Completed 3-day Urinary Voiding Diary	X		█	█	█	
Fecal Incontinence						
CCIS Questionnaire	X			X		
Completed 7-day Bowel Diary	X		█	█	█	
	█			█		
Non-Obstructive Urinary Retention						
Completed 7-day Urinary Voiding Diary	X		X	X	X***	
	█			█		
	█			█	█	█
*Must be completed prior to any study-specific procedures						
**If applicable						

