## 7.10 Safety Evaluation

All serious, device-related, procedure-related and/or therapy-related AEs and all DDs will be considered reportable for this study. All reportable AEs and DDs will be collected throughout the study once the informed consent form is signed. AEs and DDs will be coded and summarized using the Medical Dictionary for Regulatory Affairs (MedDRA). Serious AEs will be summarized for all consented subjects (Consent Subject Set), all subjects who go through lead placement procedure, as well as separately prior to INS implant (Test Subject Set) and after INS implant (Full Analysis Set). Device-related, procedure-related and/or therapy-related AEs and DDs will be summarized for all subjects who go through lead placement procedure, as well as separately prior to INS implant (Test Subject Set) and after INS implant (Full Analysis Set). For safety evaluation after INS implants, it will be summarized for subjects with INS implant only. The severity, treatment needed, resolution, and relevant principal investigator's judgment concerning the causal relationship with the devices or procedure or therapy will be provided as listing. The number of events, the number of subjects who experience an event, and the percentage of subjects who experienced one or more events will be summarized for each cohort as well as pooled for the three cohorts together. A listing of deaths and reasons for deaths will be provided for each cohort as well as pooled for the three cohorts together, if any death occur in the study.

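### Protocol 11.1 excludes symptom worsening from reportable events with no exception for serious or related cases, in conflict with its own opening rule, Protocol 15.1 and SAP 7.10

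*Protocol*

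**What the plan says.** Protocol 11.1 begins with a general rule: "Any adverse event meeting the definition of: serious adverse events and/or adverse device effects as well as all device deficiencies will be considered reportable". A study-specific note in Table 11-1 counts device-, procedure- and therapy-related events as adverse device effects. Section 11.1 also defines the therapy category: "Therapy Related: An adverse event related to therapy delivery by device e.g. device stimulation issue".

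The section then gives three items that are not adverse events. The first, expected postoperative complaints, is qualified: it applies "unless the event involves a clinically significant change in severity or duration of symptoms" or calls for care beyond the ordinary. The second covers only stimulation effects that are transient and without clinical significance. The third reads "Worsening of OAB, FI and/or NOUR symptoms will be collected as part of the study objectives and/or additional measures and are not considered" reportable, with no qualifier.

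Protocol 15.1 asks investigators to report serious events and device-, procedure- and therapy-related events, and names no exclusion for symptoms. SAP 7.10 is equally general: "All serious, device-related, procedure-related and/or therapy-related AEs and all DDs will be considered reportable for this study".

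On enrolment, Protocol 8.2 says: "Each subject will only be enrolled in one study cohort". Table 9-1 lists the visible questionnaires and diaries by cohort; for example, the row "Completed 3-day Urinary Voiding Diary" stands under OAB only.

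**The concern.** The third item removes a class of events by symptom type alone. A worsening that puts a subject in hospital, or that the investigator attributes to stimulation, falls under it just as a mild and unrelated one does. The item also names all three symptom groups without tying them to the subject's cohort.

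The safety objective (Protocol 13.7, SAP 4.4) is a summary of ADEs and serious ADEs, per cohort and pooled. An event that is never entered as an adverse event cannot appear there. Protocol 4.1 says the therapy influences the lower urinary tract, the sphincters and the colon, so a related change in bladder or bowel function is plausible on the plan's own account. Protocol 12 provides no events committee or monitoring committee, and the sponsor's medical advisor reviews reported events, so that review would not recover what the item has excluded.

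**Working it through.** The plan states no figure on this point. The check is a comparison of texts, plus simple arithmetic on cohort sizes.

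**1. One case under each rule.** Take a subject whose pre-existing bowel or bladder symptom gets worse and whose investigator judges this therapy-related.

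- Protocol 11.1, opening rule: an ADE, so reportable.
- Protocol 11.1, third item: "are not considered a reportable adverse event".
- Protocol 15.1: to be reported to the sponsor.
- SAP 7.10: to be summarised as a related event.

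Three passages point to inclusion and one to exclusion. No passage says which prevails. The same holds if the worsening is serious but unrelated, because every SAE is reportable under the opening rule.

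**2. Is the missing qualifier deliberate?** The first two items leave clinically important cases inside the reporting system, and the third does not. The first names urinary retention and constipation among expected postoperative outcomes and makes them events when they go beyond the expected. The third can be read as taking worsened retention out again.

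**3. Does capture as an outcome replace an event report?** Under Protocol 11.2 an adverse event report carries at least the date, the diagnosis or description, seriousness, relatedness, treatment and outcome. A questionnaire score or diary count carries no judgement of seriousness or relatedness and does not enter the ADE counts. Outcome capture can also fail. Permanently explanted subjects exit (Protocol 6), and the primary analysis uses subjects with baseline and 3-month data (Protocol 13.1.3). A subject who worsens and is explanted before 3 months could therefore be absent from both the main effectiveness result and the event tables. Multiple imputation is a sensitivity analysis only, used when more than 5% of data are missing (SAP 7.4).

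**4. Which symptoms are visibly measured?** Unredacted instruments in Table 9-1 and Protocol 9.5:

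- OAB: OAB-q and 3-day voiding diary.
- FI: CCIS and 7-day bowel diary.
- NOUR: 7-day voiding diary.

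Planned sizes are 60, 60 and 40, total 160. No bowel measure is visible for OAB and NOUR: (60 + 40)/160 = 100/160 = 62.5%. No bladder measure is visible for FI: 60/160 = 37.5%. OAB and NOUR both use a voiding diary, so the visible gap is between bladder and bowel.

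**5. Direction and size of the bias.** Let p be the true share of subjects with at least one ADE, and m the share whose only ADEs are of the excluded kind. The reported share is p − m, and the relative shortfall is m/p. Since m cannot be negative, the error can only be downward. The documents give neither p nor m.

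**The case against.** The best defence is that the texts can be read as consistent. The list says what is not an adverse event, and the reporting rules apply only to adverse events. On that reading there is no conflict, but the loss of serious and related worsening then becomes certain. The item's own words also refuse the status of a *reportable* event, which does not settle whether it is an event at all.

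The second defence is that lack of benefit should be counted once, as an effectiveness result. That is a fair choice for non-serious worsening of the subject's own indication that is not judged related. It does not justify removing an SAE.

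The third is redaction, and it limits the point. The additional measures of every cohort and several rows of Table 9-1 are blacked out. The reference list cites lower urinary tract symptom questionnaires whose use is not visible.

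A reader might therefore infer more than the documents support:

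- *Each cohort measures only its own symptom.* This cannot be established behind the redactions, and OAB and NOUR share a type of diary.
- *Harm outside the subject's cohort is never reportable and goes unrecorded.* The item speaks of worsening, so new onset that is serious or related can be read as reportable under the general rule. Clinically important postoperative retention is already an event under the first item. Deaths, device deficiencies and withdrawal reasons are recorded separately.
- *The understatement can be put at 7% to 25%.* This follows from m/p if one assumes p of 20% to 30% and m of 2% to 5% (0.02/0.30 = 7%; 0.05/0.20 = 25%). All four inputs are assumptions, so the range is not evidence of bias.

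**Conclusion.** The point holds as a conflict over what is reportable. As written, the third item of Protocol 11.1 excludes serious and related worsening of any of the three symptom groups, while the opening rule of the same section, Protocol 15.1 and SAP 7.10 include it. This does not depend on the redacted measures, because a score is not an event report. Where sites follow the item, ADE and serious ADE summaries are biased low. Where sites differ, counts from about 40 centres rest on different definitions. The size cannot be estimated from the documents.

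That the item's rationale is not shown across bladder and bowel is a secondary observation, conditional on the unredacted schedule. The primary effectiveness tests are not affected.

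**What to change.** Reconcile the passages. Add to the third item of Protocol 11.1, in substance: *This exclusion does not apply to worsening, of the subject's own or another indication, that meets the SAE or ADE definition. New onset of a symptom of another indication is assessed under the same SAE/ADE rule.* State the same in SAP 7.10 and in the eCRF guidance.

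The change should stop there. Making every symptom of another indication reportable, whether or not serious or related, would go beyond the study's reporting scheme. After the change the item covers only non-serious, unrelated worsening, which is not reportable anyway, so it serves as a clarification.

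The cost is a wording amendment, some additional event reports and a slightly less favourable ADE and serious ADE rate. Some worsening of the subject's own indication will count both as an event and in the effectiveness outcome. No new assessment is needed.
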